#### 4.3.2.7. All-Cause Mortality

All-cause mortality will be analyzed by investigating the relationship between all-cause mortality and treatment group. An adjusted relative risk analysis will be done using a stratified Cochran-Mantel-Haenszel test; the cross-tabulation of all-cause mortality and treatment group will be stratified by disease severity. The adjusted relative risk will be provided, along with a 90% CI.

All-cause mortality will be analyzed using the ITT population.

A by-subject data listing will be provided.

#### 4.3.2.8. Time to SARS-CoV-2 TCID50 Negative

Time to SARS-CoV-2 TCID50 negative in upper respiratory tract will be analyzed in a similar fashion as the primary efficacy endpoint. Time to SARS-CoV-2 TCID50 negative is defined as the time (in days) from initiation of study treatment (favipiravir + SOC or SOC alone) until a negative assessment in upper respiratory tract specimen.

Time to SARS-CoV-2 TCID50 negative will be performed on the mITT population.

Note: Since TCID50 for SARS-CoV-2 is not yet proven to be sensitive for detection of the virus and is still under development for that purpose, analyses using TCID50 will not be conducted if TCID50 for SARS-CoV-2 is not detectable enough.

#### 4.3.2.9. Change in SARS-CoV-2 Viral Load

The change in SARS-CoV-2 viral load in upper respiratory tract specimen as assessed by area under viral load curve (quantitative PCR) as assessed up to 29 days. The area under the curve (AUC) over time for a given subject will be calculated, using the linear trapezoidal rule, as the sum of the maximum viral load for each day up through Day 29. Lower Limit of Quantification (LLOQ) result is considered as negative. An analysis of treatment group differences will be performed on the change in viral load using ANOVA model, with treatment group and disease severity as fixed factors.

The change in SARS-CoV-2 viral load will be analyzed by comparing the change between treatment groups using a mixed model with repeated measures (MMRM). This analysis will assess whether or not there is a difference in estimated change from baseline values between active treatment and SOC by visit using least squares means estimates from the MMRM. SAS PROC MIXED will be used to fit an MMRM with change from baseline in SARS-CoV-2 viral load as the response variable and the following covariates and fixed effects:

- Baseline SARS-CoV-2 viral load (covariate)
- Treatment group (fixed effect)
- Visit (fixed effect, time will be defined in terms of Visits)
- Time by Treatment Interaction (Time\*Treatment)

The covariance structure for the repeated measures in this model will be unstructured (UN). If UN does not converge for the model, a first-order autoregressive (AR(1)) covariance structure will be used.

Changes in viral load will be analyzed using the mITT population.

By-subject data listings will also be provided.

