 - i. Fever ≤ 37.2 °C oral,
 - ii. Respiratory rate ≤ 24 /minute on room air,
 - iii. Oxygen saturation SpO2 > 94% on room air,
 - iv. Cough mild or absent on a patient reported scale of severe, moderate, mild, absent.
- 3. Clinical effect as measured by the National Early Warning Score 2 (NEWS2) system.
- 4. All-cause mortality as assessed daily up to 29 days and at final follow up on Day 60.
- 5. Frequency of respiratory progression as assessed up to 29 days (daily and per SOC at each site) and defined as:
 - a. SpO2 \leq 94% on room air or PaO2/FiO2 \leq 300mmHg, and
 - b. requirement for supplemental oxygen, or
 - c. more advanced ventilator support.
- 6. Time to defervescence (in those with fever at enrollment) as assessed daily up to 29 days and at Day 60 (if possible).
- 7. Time to cough reported as mild or absent (in those with cough at enrollment rated severe or moderate) as assessed daily up to 29 days and on Day 60.
- 8. Time to dyspnea reported as mild or absent (on a scale of severe, moderate, mild absent, in those with dyspnea at enrollment rated as severe or moderate) as assessed daily up to 29 days and on Day 60 (if possible).
- 9. Frequency of requirement for supplemental oxygen or non-invasive ventilation as assessed daily up to 29 days and on Day 60.
- 10. Time to SARS-CoV-2 RT-PCR negative in upper respiratory tract specimen as assessed up to 29 days.
- 11. Change in SARS-CoV-2 viral load in upper respiratory tract specimen as assessed by area under viral load curve as assessed up to 29 days.
- 12. Frequency of requirement for mechanical ventilation as assessed up daily to 29 days and at Day 60
- 13. Safety of favipiravir + SOC v. SOC alone as assessed daily up to 29 days and at Day 60.
- 14. C-reactive protein (CRP) over time.
- 15. Population PK analysis of favipiravir with assessment of maximum plasma concentration (C_{max}), minimum plasma concentration (C_{min}), and AUC_(0-24h) on Days 1, 2, 8 and 14.

Study Sites	Approximately 8 sites in the U.S.A.
Planned Enrollment	Approximately 50 subjects; randomized 1:1
Study Population	Adults who are hospitalized for treatment of confirmed COVID-19

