8 EFFICACY, PHARMACOKINETICS AND SAFETY ASSESSMENTS

8.1 Efficacy Assessments

Efficacy will be assessed by the following measurements:

- Presence of virus in the nasopharyngeal and oropharyngeal samples taken on Days 1, 3, 8, 11, 15 and 29 (if hospitalized and when able to return to clinic after discharge). Swabs will also be obtained on day of discharge from hospital if discharge occurs before Day 15.
- Clinical improvement of hospitalized subjects with COVID-19 receiving either favipiravir + SOC or SOC alone as defined by the following study-specific 6-point ordinal scale at Day 15

- 1. Not hospitalized
- 2. Hospitalized, not requiring supplemental oxygen
- 3. Hospitalized, requiring supplemental oxygen
- 4. Hospitalized, on non-invasive ventilation or high flow oxygen devices
- 5. Hospitalized, on invasive mechanical ventilation or ECMO
- 6. Death
- Status on the study specific 6-point ordinal scale assessed daily while hospitalized and at each outpatient visit until Day 60.
- NEWS2 assessed daily while hospitalized and at each outpatient visit until Day 60.
- Patient status assessed daily while hospitalized and at each outpatient visit until Day 60 via Study-specific Symptom Status and the ECOG Performance Status questionnaires (see Appendix A).
- Duration of supplemental oxygen (if applicable).
- Duration of mechanical ventilation (if applicable).
- Duration of hospitalization.
- Date and cause of death (if applicable).
- PCR and TCID50 in nasopharyngeal and oropharyngeal swabs on Days 1, 3, 8, 11, 15 and 29 (if hospitalized and when able to return to clinic after discharge), and on day of discharge if hospital discharge occurs before Day 15.
- Blood for determination of antibodies to SARS-CoV-2 obtained on Days 1, 15 and 29 (if hospitalized and when able to return to clinic after discharge).

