9.6 Efficacy Endpoint Analysis

The primary endpoint of time to viral clearance will be analyzed with the log-rank test for treatment difference and summarized using the Kaplan-Meier methodology as noted above. Viral load results from day of discharge as available will also be included in the analysis of viral clearance.

The key secondary endpoint of status of clinical recovery as measured by the study-specific 6-point ordinal scale at Day 15 will be analyzed using ordinal categorical data methods, since it is unlikely that linear differences exist between the elements of the scale (for example, a 1-point difference in magnitude may not apply to each increment on the scale). As an exploratory analysis, sequential binary analysis will be performed, based on successive classification of a subject into categories of less than or greater/equal to each ordinal item on the scale. Longitudinal analysis of the 6-point scale over time on study will also be performed to investigate temporal patterns of improvement.

Time to event endpoints will be analyzed using similar methods as used for the primary endpoint; these will include time to: clinical recovery; defervescence; cough mild or absent; dyspnea mild or absent; SARS-CoV-2 RT-PCR negative in upper respiratory tract.

Categorical endpoints will be analyzed using categorical data analysis methods; continuous data will be analyzed using analysis of variance with treatment and strata as factors.

Missing efficacy data in a trial of hospitalized patients is generally unlikely, and great care will be taken at each study site to ensure that all outcome assessments are obtained as planned in this protocol. However, as treatment of COVID-19 subjects evolves, it is clear some subjects will be discharged from the hospital prior to Day 15. Subjects are asked to return for follow up visits on Days 29, 45 and 60. This requirement is presenting challenges for subjects and in order to ensure that in cases where the subject does not return for their follow up visits, an additional swabbing has been added on the day of hospital discharge (See Section 7.7). Should missing data occur for the primary endpoint, time to viral clearance, such patients will be included in the log-rank analysis as censored observations. Missing clinical outcome data will be evaluated using a variety of methods, including multiple imputation, worst-value assignment, and other methods, to be completely outlined in the statistical analysis plan.

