| ECOG Performance
Status                               | X                 |   | X     | X     | X     | X      | X      | X                                       | X                  | X   |  |
| Study Specific
Symptom Status                         | X                 |   | X     | X     | X     | X      | X      | X                                       | X                  | X   |  |
| Randomization  | X                 |   |       |       |       |        |        |   |                    |   |  |
| Investigational Product
Dosing                                    |                   | Favipiravir Dosing Days 1-14
(1800mg BID on Day 1000mg BID Days 2-14)  |       |       |       |        |        |   |                    |   |  |
| Solicitation of
Treatment-Emergent
Adverse Events  |                   | X   | X     | X     | X     | X      | X      | X                                       | X                  | X   |  |
| Release from the Study   |                   |   |       |       |       |        |        |   |                    | X   |  |

1. Hematology, Chemistry (See Protocol Section 8.4).
2. May use results of labs taken at the hospital as part of SOC if done no more than 24 hours prior.
3. To be measured every day while hospitalized and at each clinic visit after hospital discharge through Day 60
  - a. Vital signs
  - b. Clinical Status 6-point scale
  - c. NEWS2
  - d. ECOG Performance status
  - e. Study-specific symptom status
  - f. Adverse Events
  - g. SpO2
  - h. Limited PE (heart and lungs)
4. PK on Day 1 prior to favipiravir dosing and between 45 to 75 minutes post-first dose.

5. PK trough samples to be taken approximately 30 minutes prior to any dose.
6. PK peak samples to be taken between 45 and 75 minutes post-dose.
7. Maintenance dose for CP score A is 800mg BID.
8. Days 45 and 60 may be completed in the hospital, outsubject clinic or by phone.
9. Subjects will undergo 9 planned venipunctures.
10. To be completed by PI or designee.
11. Days 3, 8, 11 Nasopharyngeal and Oropharyngeal Swabs for Viral RNA, PCR, and TCID50 may be done +/- 1 day from their scheduled day. Swabs will also be obtained on day of discharge from hospital if discharge occurs before Day 15.
12. To be checked throughout hospitalization and at clinic visits and changes only recorded as applicable.

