## 1.2.6. Efficacy, Pharmacokinetic, and Safety Parameters

### 1.2.6.1. Efficacy Parameters

Efficacy will be measured through the following parameters:

For Primary Endpoint:

- PCR in the nasopharyngeal and oropharyngeal samples taken on Days 1, 3, 8, 11, 15 and 29. Swabs will also be obtained on day of discharge from hospital if discharge occurs before Day 15.

For Secondary Endpoint:

- Clinical improvement of hospitalized subjects with COVID-19 receiving either favipiravir + SOC or SOC alone as defined by the following study-specific 6-point ordinal scale assessed daily while hospitalized and at each outpatient visit until Day 60..
  1. Not hospitalized
  2. Hospitalized, not requiring supplemental oxygen
  3. Hospitalized, requiring supplemental oxygen
  4. Hospitalized, on non-invasive ventilation or high flow oxygen devices
  5. Hospitalized, on invasive mechanical ventilation or ECMO
  6. Death
- NEWS2 assessed daily while hospitalized and at each outpatient visit until Day 60.
- Vital signs (BP, HR, RR, BT, SpO2) measured daily while hospitalized and at each outpatient visit until Day 60.
- Patient status assessed daily while hospitalized and at each outpatient visit until Day 60 via Study-specific Symptom Status and ECOG Performance Status questionnaires
- Period of each respiratory assistance (if applicable).
- Period of hospitalization.
- Period of intensive care unit (if applicable).
- Date and cause of death (if applicable).
- TCID50 in nasopharyngeal and oropharyngeal swabs on Days 1, 3, 8, 11, 15 and 29. Swabs will also be obtained on day of discharge from hospital if discharge occurs before Day 15.

Note: Since TCID50 for SARS-CoV-2 is not yet proven to be sensitive for detection of the virus and is still under development for that purpose, analyses using TCID50 will not be conducted if TCID50 for SARS-CoV-2 is not detectable enough.
- Blood for determination of antibodies to SARS-CoV-2 obtained on Days 1, 15 and 29.

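### SAP 4.3.2.9 defines the viral-load AUC both by the trapezoidal rule and as a sum of daily maxima; the sum is not an area and shifts with the number of swabs.

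*SAP*

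**What the plan says.** The protocol synopsis lists this secondary endpoint: "Change in SARS-CoV-2 viral load in upper respiratory tract specimen as assessed by area under viral load curve as assessed up to 29 days".

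SAP 4.3.2.9 gives the calculation in one sentence. It opens with "The area under the curve (AUC) over time for a given subject will be calculated, using the linear trapezoidal rule" and ends with "as the sum of the maximum viral load for each day up through Day 29". It adds "Lower Limit of Quantification (LLOQ) result is considered as negative" but gives no number for such a result. An ANOVA with treatment group and disease severity follows. Its response is described only as the change in viral load, so the AUC is not named. A separate MMRM of change from baseline by visit does not use the AUC.

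On sampling, SAP 1.2.6.1 specifies "PCR in the nasopharyngeal and oropharyngeal samples taken on Days 1, 3, 8, 11, 15 and 29". Footnote 11 of SAP Table 1-1 adds: "Swabs will also be obtained on day of discharge from hospital if discharge occurs before Day 15". Protocol 8.1 makes the swabs conditional: "if hospitalized and when able to return to clinic after discharge". Protocol 9.6 accepts that "it is clear some subjects will be discharged from the hospital prior to Day 15" and that return visits are proving difficult.

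SAP section 5 lists no change to this endpoint, so the sum is not a declared departure from the protocol.

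**The concern.** One sentence gives two rules for one number. On a log10 scale, a trapezoid has units of log10 × days and a sum of values has units of log10. Two programmers could each follow the sentence and report different results, and only the trapezoid is the area that the protocol names.

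The schedule makes the difference matter. Swabs are few and unevenly spaced, and their number varies by subject: discharge before Day 15 can add one, and failure to return removes later ones. The trial is open label, so discharge timing, and with it swab count, could differ by arm. A plain sum would carry such a difference into a virologic comparison intended to inform Phase 3.

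**Working it through.** The documents give no numerical value for the AUC, so there is no planned figure to reproduce. The sample size of 50 rests on the log-rank test of the primary endpoint. All loads below are illustrative log10 values, with negative set to 0.

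**Weights.** Trapezoid = Σ (tᵢ₊₁ − tᵢ)(vᵢ + vᵢ₊₁)/2. On Days 1, 3, 8, 11, 15 and 29 the six values get weights of 1, 3.5, 4, 3.5, 9 and 7 days (total 28). The sum gives each a weight of 1.

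**Two profiles.**

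- Fast clearer (6, 5, 3, 0, 0, 0): trapezoid 11 + 20 + 4.5 = 35.5; sum 14.0.
- Slow clearer (6, 5.5, 4.5, 4, 3, 0): trapezoid 11.5 + 25 + 12.75 + 14 + 21 = 84.25; sum 23.0.

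With equal swabs, both rules put the two subjects in the same order.

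**Added swab.** A Day 4 discharge swab on the fast clearer's own line is 5 − 0.4 = 4.6. The trapezoid stays at 35.5; the sum becomes 14.0 + 4.6 = 18.6.

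**Same course, different swab counts.** The load falls 0.4 log10 per day from 6 on Day 1 (true area 6 × 15/2 = 45.0).

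| Swabs | Sum | Trapezoid |
|---|---|---|
| Full schedule (6) | 16.8 | 47.6 |
| Plus Day 5 discharge swab (7) | 21.2 | 47.6 |
| Day 8 missed (5) | 13.6 | 47.6 |

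The trapezoid does not move here because the course is straight across those days. Where it bends, a missed swab moves the trapezoid too: at 0.8 per day, missing Day 8 takes it from 23.0 to 28.0 (true area 22.5), and the sum from 10.8 to 10.4.

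**Ranking and scale.** The slow clearer last swabbed on Day 8 has sum 6 + 5.5 + 4.5 = 16.0, below the fast clearer's 18.6 with the Day 4 swab, so the order reverses. On the raw scale the same profiles give about 1.14 million for the fast clearer (10⁶ + 10⁵ + 10^4.6 + 10³) and 1.35 million for the slow one (10⁶ + 10^5.5 + 10^4.5), and there is no reversal.

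**Early last swab.** The slow clearer stopped at Day 8 has trapezoid 11.5 + 25 = 36.5 instead of 84.25. Dividing by observed time does not repair this kind of truncation. The fast clearer last swabbed on Day 4 averages (11 + 4.8)/3 = 5.27, against 35.5/28 = 1.27 with full follow-up and 84.25/28 = 3.01 for the fully followed slow clearer.

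**How much of the sum is load.** A simulation assumed a starting load of 6 (SD 1.2), decline of 0.4 per day (SD 0.12), 20% of post-baseline visits missed and 60% of subjects with a discharge swab. The sum correlated 0.85 with true area and 0.36 with swab count; the trapezoid correlated 0.95 and 0.03.

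**The case against.** The strongest reply is that the sentence names the trapezoid first and that two specimens are taken on each swab day. The daily maximum may therefore mean the higher of the nasopharyngeal and oropharyngeal results, used as input to the trapezoid. That reading is coherent and may be what was intended, but the SAP does not state it.

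A second reading interpolates loads to every day from 1 to 29. The daily sum then equals the trapezoid plus half the first and last values: 38.5 against 35.5 for the fast clearer and 87.25 against 84.25 for the slow one. Order is kept. The SAP does not mention interpolation.

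Other sections might also limit the harm. The visit windows in SAP 3.11 keep one value per window, which could drop a discharge swab, but they apply to by-visit analyses and the AUC sentence speaks of each day. The multiple imputation in SAP 3.10.1 covers missing clinical outcome data for secondary endpoints other than time-to-event. Section 4.3.2.9 does not say whether missing swabs or the AUC fall under it.

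A reader might infer that the sum measures swab count instead of viral exposure. The figures do not support that: with six swabs each, the profiles sum to 14.0 and 23.0, and zeros after clearance add nothing. A reader might also infer that subjects will be misranked or the arm comparison biased. The documents give no viral loads, no load scale and no discharge or return rates by arm, so neither is shown.

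**Conclusion.** The conflict in the wording is real and should be corrected. On the literal reading, the sum is not the protocol's area and depends partly on how many swabs a subject had: 14.0 to 18.6 for one added swab, and 13.6 to 21.2 across five to seven swabs on one course, with the trapezoid unchanged in both cases. These sizes rest on assumed log10 loads. Rank reversal is possible on that scale but is absent on the raw scale for the same profiles.

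Deleting the sum clause is necessary but not sufficient, because the trapezoid is itself distorted when swabs stop early (36.5 against 84.25).

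The reach is limited. This is a secondary endpoint, and SAP 3.2 makes every p-value other than the primary one descriptive.

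**What to change.** In SAP 4.3.2.9, replace "as the sum of the maximum viral load for each day up through Day 29" with a full definition to Day 29:

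- The value for a day is the higher of the nasopharyngeal and oropharyngeal results.
- These values enter a linear trapezoid over actual swab days, including any discharge swab, on a named scale (for example log10).
- Negative and LLOQ results take a stated number.
- This AUC is the response in the ANOVA.
- A stated rule covers a last swab before Day 29, including whether SAP 3.10.1 imputation applies, and a sensitivity analysis checks it.

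Do not divide by observed time for subjects with an early last swab, because that makes fast clearers who are discharged early and do not return look worse.

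The cost is a few lines of SAP text and one added sensitivity analysis. No new data are needed.

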9.5 Stratification, Subgroup Analysis and Pooled Analysis

The stratification factors used in randomization, critical v. severe v. mild/moderate disease as defined above based on supplemental oxygen requirements, SpO2 status etc., will be accounted for in the efficacy analyses. The stratification factor may be deleted from the statistical model if the interaction is not significant at the 0.10 level. Efficacy data will be pooled across study sites for analysis, after visual inspection of summary results reveals similarity across study sites. Efficacy results may also be summarized within each randomization stratum for exploratory purposes.

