### **3.7. Adjustments for Covariates**

For the analyses of durations of supplemental oxygen, non-invasive/mechanical ventilation, Extracorporeal Membrane Oxygenation (ECMO), hospitalization, and ICU, baseline SpO2 level will act as a covariate in all analysis of covariance (ANCOVA) models. Disease severity, as defined in [Section 1.2.2](#), will be accounted for in all efficacy analyses. Other factors may be accounted for if deemed relevant.

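### The viral-load MMRM leaves out disease severity, contrary to SAP 3.7; the ANOVA beside it breaks no rule but loses precision by leaving out baseline viral load

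*SAP*

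**What the plan says.** SAP 4.3.2.9 describes two analyses of quantitative PCR.

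- **ANOVA.** The section defines an area under the viral-load curve up to Day 29, then plans to test the "change in viral load using ANOVA model, with treatment group and disease severity as fixed factors". Baseline load is not a term.
- **MMRM.** The response is change from baseline. The listed terms start with "Baseline SARS-CoV-2 viral load (covariate", continue with treatment and visit, and end with the time-by-treatment interaction. Severity is not a term.

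Both use the mITT set: "Changes in viral load will be analyzed using the mITT population".

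The general rule is in SAP 3.7: disease severity "will be accounted for in all efficacy analyses". The only baseline measurement that SAP 3.7 names as a covariate is SpO2, for the models of duration of respiratory support, hospitalization and ICU stay.

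Protocol 9.6 says that "continuous data will be analyzed using analysis of variance with treatment and strata as factors". Protocol 9.5 adds an option: "The stratification factor may be deleted from the statistical model if the interaction is not significant at the 0.10 level". The SAP does not repeat that option. SAP Section 5 lists one change from the protocol, the removal of hierarchical testing.

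**The concern.** Two neighbouring models of the same data each leave out what the other includes, and no reason is given. The two omissions differ in kind.

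For the MMRM the issue is contradiction. SAP 3.7 requires severity and the term list does not have it, so two programmers could each defend a different model. Severity is also a randomization stratum, and leaving a stratum out of the model tends to make standard errors slightly too large.

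For the ANOVA the issue is precision. A baseline swab is scheduled before dosing on Day 1, so the covariate needs no new data. If the response is the AUC, the baseline value is also its starting point. Randomization is stratified by site and severity, so nothing balances baseline load between arms. With about 25 per arm, a chance difference would pass in part into the estimated treatment effect.

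**Working it through.** **What the plan gives.** The documents state no SD, correlation, sample size or power for viral load. The only stated size, 25 per arm with 90% power at two-sided alpha 0.10, is for the log-rank test (SAP 3.1). It reproduces well enough to serve as the basis here:

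- Exponential medians of 4 and 11 days give a rate ratio of 11/4 = 2.75.
- Clearance by Day 15 is 1 − 2^(−15/4) = 0.926 and 1 − 2^(−15/11) = 0.611, mean 0.769.
- 50 subjects give 38.4 events. Power is 89.4% by Freedman's formula and 93.2% by Schoenfeld's.

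**Which model meets which rule.**

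| Model | Severity | Baseline load | SAP 3.7 (severity) | Protocol 9.6 (treatment and strata) |
|---|---|---|---|---|
| ANOVA | yes | no | met | met |
| MMRM | no | yes | not met | severity stratum missing |

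The option in Protocol 9.5 does not rescue the MMRM. It depends on the result of an interaction test, whereas here the factor is absent from the start, and the SAP does not carry the option over.

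**Baseline load in the ANOVA, response = AUC.** Let rho be the correlation between baseline and AUC within arm and severity (assumed). Residual variance is multiplied by 1 − rho², and the equivalent increase in sample size is 1/(1 − rho²) − 1. For power, assume an effect with 80% power unadjusted: (1.645 + 0.842) × √(2/25) = 0.70 SD. The last column includes an approximate cost of one parameter, a variance factor of 1 + 1/45.

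| rho | Variance ratio | SE ratio | Equivalent extra subjects | Power |
|---|---|---|---|---|
| 0.3 | 0.91 | 0.95 | 10% | 82.5% |
| 0.5 | 0.75 | 0.87 | 33% | 88.4% |
| 0.7 | 0.51 | 0.71 | 96% | 96.4% |

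The standard error of a chance baseline difference is √(2/25) = 0.28 SD. At rho = 0.5, an imbalance of that size moves the unadjusted AUC difference by 0.5 × 0.28 = 0.14 SD, one fifth of the assumed 0.70 SD effect.

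**Baseline load in the ANOVA, response = simple change score.** With equal variances at the two times, the change score has variance 2(1 − rho) and the ANCOVA 1 − rho², so the ratio is (1 + rho)/2. For rho = 0.3, 0.5, 0.7 it is 0.65, 0.75, 0.85. The gain now shrinks as rho rises, so the size of the benefit depends on which response is meant.

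**Severity in the MMRM.** This is a rough illustration for one visit contrast with the same 0.70 SD effect. Severity has three levels and costs two parameters, a variance factor of 1 + 2/44.

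| Share of remaining variance explained by severity (assumed) | Power |
|---|---|
| 0 | 78.4% |
| 0.02 | 79.2% |
| 0.05 | 80.2% |
| 0.10 | 82.1% |
| 0.20 | 85.9% |

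Against 80% without severity, there is no gain until severity explains about 5% of the variance left after baseline.

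**The case against.** Several things can be said for the plan as written.

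- **The section already covers both factors between its two models.** A baseline imbalance is handled by the MMRM and severity by the ANOVA. This is partly right, but the MMRM does not adjust the AUC, and SAP 3.7 says all efficacy analyses, not one of each pair. The primary log-rank test is itself unstratified, but a stratified sensitivity analysis accompanies it; the MMRM has no counterpart with severity.
- **Randomization makes the comparison unbiased without covariates.** True. Only precision and chance imbalance are at issue.
- **The gains are assumed.** True. They rest on correlations that the documents do not give, and on reading an unclear response as the AUC.
- **The data set is small.** True. The mITT set is at most about 50, the MMRM starts from an unstructured covariance, and the SAP already plans for non-convergence. This argues against adding a baseline-by-visit term as a requirement: over the five scheduled post-baseline swab days it would cost 4 more parameters, and no rule in the SAP calls for it.
- **A baseline value is scheduled, not assured to be informative.** True. SAP 2.1 admits to mITT a subject who is positive in any protocol-required swab, so the Day 1 result may be negative or below the quantification limit.

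A reader might infer that both models break SAP 3.7. They do not: the severity rule is met by the ANOVA, and no passage requires baseline viral load there.

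**Conclusion.** The MMRM term list contradicts SAP 3.7, and the departure is undeclared. That rests on the text alone and is firm. Its numerical effect is probably small and may be nil.

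The ANOVA is compliant but less efficient than it could be. For the AUC, the reduction in residual variance is 9% to 49% for assumed correlations of 0.3 to 0.7. For a simple change score with equal variances it is 35% to 15% over the same range. Neither range can be narrowed from the documents, and both assume 25 evaluable subjects per arm.

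A reader might also infer that the trial's main antiviral evidence is at risk. The documents do not support that. This is secondary endpoint 11, SAP 3.2 makes every p-value except the primary one descriptive, and the log-rank test of time to clearance does not use these models. The point is worth fixing because the study is meant to inform a Phase 3 trial and the change is cheap, not because a conclusion depends on it.

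**What to change.** Amend SAP 4.3.2.9 before database lock, so that in an open-label trial the choice cannot look data-driven.

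1. Add disease severity to the MMRM as a fixed effect (2 degrees of freedom). If the sponsor prefers to leave it out, declare that in Section 5 and qualify Section 3.7.
2. Add baseline log10 viral load to the ANOVA, making it an ANCOVA with treatment, severity and baseline (1 degree of freedom). State the value used for a negative or below-limit baseline result.
3. Say whether the ANOVA response is the AUC or a change from baseline.

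A baseline-by-visit term is optional. The cost is two model statements and one definition, with no new data.
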